7. PLANNED ANALYSIS

For End-Of-Text (EoT) tables, the set of summary statistics is: N / Mean / SD / Min //Q1/ Median /Q3/ Max.

For tables that are provided for endpoints with some extreme data, median, quartiles and percentiles should be preferred to mean, standard deviation, minimum and maximum.

Tabulations of frequencies for categorical data will include all possible categories and will display the number of observations in a category as well as the percentage (%) relative to the respective treatment group (unless otherwise specified, all subjects in the respective subject set whether they have non-missing values or not).

The precision for percentages should be one decimal point, unless the denominator is smaller than 100 (in all treatment columns), in which case percentages are given in integer numbers. The category missing will be displayed only if there are actually missing values.

7.1 DEMOGRAPHIC AND OTHER BASELINE CHARACTERISTICS

Only descriptive statistics are planned for this section of the report.

Demographic data and baseline characteristics will be summarised. For some continuous variables, the following categories will be defined and presented according to the number and percentage of patients in each category (Table 7.1: 1):

 Table 7.1: 1
 Categories for summary of continuous variables

Variable	Categories
Age	< 65 years 65 to <=74 years ≥ 75 years
BMI	< 18.5 kg/m ² 18.5 to <25 kg.m ² 25 to < 30 kg/m ² \ge 30 kg/m ²
Time since first diagnosis of Non IPF Pulmonary Fibrosis or IPF	< 1 year 1 to < 3 years 3 to 5 years > 5 years
Time since first diagnosis of Non IPF Pulmonary Fibrosis	< 1 year 1 to < 3 years 3 to 5 years > 5 years

The following demographics and baseline characteristics will be tabulated:

Demographic characteristics:

Boehringer Ingelheim TSAP for BI Trial No: 1490-0005

Proprietary confidential information © 2024 Boehringer Ingelheim International GmbH or one or more of its affiliated companies

- Sex
- Gender identity
- Ethnicity
- Race
- Country
- Age(continuous, category)

- Tobacco use
- Weight(continuous, category)
- Height
- Body Mass Index (continuous, category)

Baseline characteristics (including spirometry):

- Time since diagnosis IPF or Non IPF Pulmonary Fibrosis(continuous, category)
- Time since diagnosis Non IPF Pulmonary Fibrosis (continuous, category)
- Underlying ILD diagnosis
- Historical HRCT pattern
- ILD progression information within the last 12 months

- Spirometry:
 - Forced Expiratory Volume in 1 Second (FEV1)
 - Percent Predicted FEV1
 - Forced Vital Capacity (FVC)
 - Percent Predicted FVC
 - FEV1/FVC
 - Percent Predicted FEV1/FVC
 - Forced Expiratory Flow 25-75%
 - Peak Expiratory Flow (PEF)
 - Forced Inspiratory Vital Capacity (FIVC)

7.2 CONCOMITANT DISEASES AND MEDICATION

Concomitant diseases (i.e. baseline conditions) and concomitant non-drug therapies will be coded according to the most recent version of MedDRA. Concomitant medications will be coded according to the most recent version of the World Health Organisation – Drug Dictionary.

Only descriptive statistics are planned for this section of the CTR. Analyses of concomitant diseases and medications will be based on the TS.

Baseline conditions and diagnosis will be summarised with frequency and percentage of patients by SOC and preferred name.

Concomitant medication use will be summarised with frequency and percentage of patients by ATC3 class and preferred name. The following summaries will be presented by medication used for cough (yes, no):

- Baseline medications: starting prior medication taken any time prior to Day 1 and continuing into the study period
- Concomitant medications: starting any time during the study period

A separate summary of baseline and concomitant anti-tussive medications, angiotensinconverting enzyme (ACE) inhibitors, opiates, and systemic or inhaled (excluding intranasal) corticosteroids will also be produced.

Concomitant procedures/non-drug therapies will be summarised with frequency and percentage of patients.

7.3 TREATMENT COMPLIANCE

Not applicable, no treatment is given in this trial.

7.4 PRIMARY ENDPOINT(S)

7.4.1 **Primary analysis of the primary endpoint(s)**

CTP Section 7.2.3: The cough count (CC) frequency, measured over 4 24-hour recordings in 12 weeks will be analysed as CC/hour and will be log-transformed for data summaries. On each day for which cough monitoring is completed, the log-transformed cough count is calculated as:

Log-transformed cough count = $log \frac{Number of coughs}{Length of readable recorded time (hours)}$

Cough count for each visit will be reported descriptively. Summary statistics will be tabulated on original scale of CC/hr as well as the geometric mean and 95% confidence intervals after back-transforming the summarized log transformed data.

Summary measurements and individual values of CC/hr over time will also be presented graphically.

Descriptive statistics, including the coefficient of variation (CV), for cough count/hour will be tabulated by visit using the original scale and for the log (natural) transformed values. In cases where 0 coughs are observed during a recording interval (e.g. night time, low activity duration, or over the 24 hour recording period), 0.1/hr will replace 0 in order to allow for the log transformation. Geometric means, coefficients of variation and 95% CIs be presented as well. For these, the summary measures using the log-transformed values will be calculated then back-transformed to the original scale.

Boehringer Ingelheim TSAP for BI Trial No: 1490-0005

Proprietary confidential information © 2024 Boehringer Ingelheim International GmbH or one or more of its affiliated companies

Plots of the geometric means and geometric mean ratios over time will be produced. Individual time profiles for CC/hr will also be presented graphically.

The primary endpoints will be summarized in the same fashion as described above by each subgroup level listed in Section 6.4.

7.5 SECONDARY ENDPOINT(S)

7.5.1 Key secondary endpoint(s)

This section is not applicable as no key secondary endpoint has been specified in the protocol.

7.5.1.1 Primary analysis of the key secondary endpoint(s)

This section is not applicable as no key secondary endpoint has been specified in the protocol.

7.5.2 (Other) Secondary endpoint(s)

CTP Section 7.2.3.1: Secondary endpoints will be summarized descriptively by visit.

Change from baseline in CC/hr at Week 4, Week 8, and Week 12 will be summarized in terms of absolute changes in CC/hr and in terms of geometric mean ratios. Model based estimates for changes from baseline at Week 12, for example least squares means adjusted for baseline CC/hr or other covariates, may be calculated.

Standard descriptive statistical parameters will be tabulated for all other secondary endpoints.

To assess the relationship between objective cough frequency and FVC (mL), correlations (spearman and Pearson) will be calculated between the following variables:

- Baseline CC/hr (log-transformed) and Baseline FVC (mL)
- Baseline CC/hr (log-transformed) and FVC (mL) at Week 12
- Baseline CC/hr (log-transformed) and change from baseline FVC (mL) at Week 12
- CC/hr at Week 12 (log-transformed) and FVC (mL) at Week 12
- Change in CC/hr at Week 12 (calculated from log-transformed values) and change from baseline in FVC (mL) at Week 12

Graphical presentations of the secondary endpoints and correlations may also be produced.

Changes from baseline in CC/hr (absolute changes on the original scale and geometric mean ratios calculated from the log transformed values) at each visit will be presented along with the primary endpoints in the descriptive tabulations. Additionally, geometric mean ratios at Weeks 4, 8 and 12, and 95% CIs will be calculated using a statistical model adjusting for the baseline CC/hr. This model can be described as follows:

$$y_{ij} = \mu + v_j + b_i + e_{ij},$$

where

- $\mathbf{y_{ij}}$ Log(CC/hr at Visit j) Log(baseline CC/hr) for patient i,
- μ overall intercept,
- v_i jth Visit (e.g. Week 4, Week 8, Week 12)
- b_i Log(baseline CC/hr) for subject i,
- e_{ii} the random error associated with subject i at visit j.

The adjusted means, standard errors, lower and upper 95% confidence limits from the above model will then be back-transformed and presented as the geometric mean ratios, geometric standard errors and 95% confidence limits.

Study feasibility endpoints:

• Feasibility of remote cough data capture (defined as % of analysable data per 24-hour recording)

The % of analysable data per 24-hour recording period will be derived from the cough count recording times(Total readable recording time) and defined as:

Total readable recording time

24 (hours)

- x 100

Descriptive statistics will be produced by visit as well as the number and percentage of patients who have $\geq 80\%$ (19.2 hrs) of analyzable data.

• Feasibility of hybrid study design (successful completion of all elements of remote visit)

Successful completion of a remote visit will be based on the questions on the home study procedures eCRF:

- Was home spirometry performed? (Visit 3, Visit 4, Visit 5, Visit 6)
- Was the videoconference televisit completed? (Visit 4, Visit 5)
- Was the 24 hour cough recording completed? (Visit 3, Visit 4, Visit 5)

The number and percentage of patients who complete each element will be tabulated by visit as well as the number an percentage of patients who complete all elements by visit.

Correlation analyses:

Sample Spearman and Pearson correlation coefficients for the pairs of CC/hr and FVC measurements listed above along with the associated p-values to assess the relationship between objective cough frequency and FVC (mL), correlations will be calculated. Scatter plots for the pairs of variables will also be produced.

Boehringer Ingelheim

 TSAP for BI Trial No: 1490-0005
 Page 19 of 27

 Proprietary confidential information © 2024 Boehringer Ingelheim International GmbH or one or more of its affiliated companies

001-MCS-50-415_RD-01 (3.0) / Saved on 18 Jan 2021

Boehringer Ingelheim TSAP for BI Trial No: 1490-0005

Proprietary confidential information © 2024 Boehringer Ingelheim International GmbH or one or more of its affiliated companies

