2.1 MAIN OBJECTIVES, PRIMARY AND SECONDARY ENDPOINTS

2.1.1 Main objectives

The primary objective of this study is to objectively describe cough frequency, utilizing four 24-hour cough recordings over 12 weeks in a cohort of subjects with Non IPF Pulmonary Fibrosis or IPF using the cough monitor.

The secondary objectives for this study are:

- Assess the relationship between objective cough frequency and FVC (mL)
- Assess feasibility of patient performed remote cough data upload
- Assess feasibility of hybrid study design (% successful completion of remote visits)

2.1.2 **Primary endpoint(s)**

Primary Endpoints: Cough count per hour (CC/hr) measured over a 24-hour period at baseline visit, Week 4(V4), Week 8(V5), Week 12 (V6).

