3.3.4 Discontinuation of patients from assessments

Patients may discontinue study participation or withdraw consent to study participation at any time ("withdrawal of consent"). If the patients agree, they should stay in the study. Even if continuing to wear the cough monitor is not possible, they should attend further study visits to collect important study data.

An individual patient will discontinue the study if:

- The patient has repeatedly shown to be non-compliant with important study procedures and, in the opinion of both, the investigator and contracting entity representative, is not willing or able to adhere to the study requirements in the future.
- The patient can no longer perform the study procedures for medical reasons

Measures to control the withdrawal rate include careful patient selection, appropriate explanation of the study requirements and procedures prior to study enrolment, as well as the explanation of the consequences of withdrawal.

The decision to discontinue or withdraw consent to study participation and the reason must be documented in the patient files and CRF.

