4.2.2.3 Contraception requirements

No contraception requirements are necessitated by use of the device.

4.3 **DEVICE USE COMPLIANCE**

Compliance with cough recordings will be assessed based on patient adherence to cough monitoring (defined as % of time over the 24-hour recording period that the patient is wearing the cough monitor) and remote cough data capture (defined as % of analyzable data per 24-hour recording).

Site staff will receive notification via email each time a patient completes a cough count recording with successful data upload. If the site does not receives this type of notification, the site should contact the patient to assess whether the patient requires assistance with any elements of the 24 hour cough recording and upload.

Page 25 of 71

Proprietary confidential information © 2022 Boehringer Ingelheim International GmbH or one or more of its affiliated companies

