7.3 HANDLING OF MISSING DATA

Imputation of missing data will not be done. Unless otherwise noted, analysis will be conducted using all patients with the endpoint available.

Missing or incomplete AE dates will be imputed according to BI standards.

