6.6 HANDLING OF MISSING DATA AND OUTLIERS

The following approaches will be applied in this trial:

- The original results (OR) approach implies the presentation of data exactly as observed (not using time windows as described in Section 6.7 and not setting values to missing). OR analysis will be performed on parameters and endpoints for which it is not meaningful to apply any imputation rule for the replacement of missing values.
- Observed cases (OC) approach will include all collected data, without imputation for any missing data after applying the time windows as described in Section 6.7

Missing or incomplete AE dates are imputed according to BI standards.

Other partial start and stop dates, for example, concomitant medications, non-drug therapies, and IPF diagnoses will be imputed to enable subsequent calculation (but not for display) by the following approach:

- If the day of the end date is missing, then the end date is set to last day of the month (or to the patient's end of study participation from End of Study eCRF. if it is earlier than the last day of the month).
- If the day and month of the end date are missing then the end date is set to 31st of December of the year (or to the patient's end of study participation from End of Study eCRF, if it is earlier than the 31st of December of the year).

Boehringer Ingelheim TSAP for BI Trial No: 1490-0005

Proprietary confidential information © 2024 Boehringer Ingelheim International GmbH or one or more of its affiliated companies

- If the day of the start date is missing the start date is set to first day of the month.
- If the day and month of the start date are missing then the start date is set to 1st January of the year.
- All other cases need to be assessed by the trial team on an individual basis, using the above points as guidance.

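### The by-visit mean, median and quartiles of % analysable cough data leave out recordings never made or uploaded, so they overstate upload feasibility; no endpoint counts uploads

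*SAP*

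**What the plan says.** Protocol 2.1.1 sets the secondary objective: "Assess feasibility of patient performed remote cough data upload". The endpoint that serves it (Protocol 2.1.3, SAP 5.2.2) is the percentage of analysable data per 24-hour recording.

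SAP 7.5.2 introduces the formula with these words: "The % of analysable data per 24-hour recording period will be derived from the cough count recording times(Total readable recording time) and defined as". The formula divides the readable hours of a recording by 24 and multiplies by 100. It plans two summaries: "Descriptive statistics will be produced by visit as well as the number and percentage of patients who have" at least 80% (19.2 hours) of analysable data.

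On missing values, Protocol 7.3 says: "Imputation of missing data will not be done. Unless otherwise noted, analysis will be conducted using all patients with the endpoint available". SAP 6.6 offers two approaches. One presents data as observed. The other is described as: "Observed cases (OC) approach will include all collected data, without imputation for any missing data", once visit windows have been applied. The SAP does not say which applies to this endpoint, and neither gives a value to a recording that does not exist.

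On denominators, SAP section 7 takes percentages in categorical tables relative to the "respective treatment group (unless otherwise specified, all subjects in the respective subject set whether they have non-missing values or not"). SAP 6.3 names the Entered Set for secondary endpoints.

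A second feasibility endpoint in SAP 7.5.2 uses an eCRF question on whether the 24-hour recording was completed, listed for Visits 3, 4 and 5. The flow chart and Protocol 6.1 schedule recordings at Visits 2, 4, 5 and 6.

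**The concern.** The question is whether patients can record at home and get the data to the platform. According to Protocol 1.2 and 5.1, data pass from the biosensor through the app to the platform and are annotated there. A recording not made, or made and not uploaded, therefore yields no readable time. With no imputation and a restriction to patients who have the endpoint, such a recording is absent from the mean, median and quartiles. These then describe data yield given that a recording arrived.

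Absent recordings are foreseen. Protocol 3.3.4 asks patients to stay in the study even when they can no longer wear the monitor. One ground for discontinuation is: "The patient has repeatedly shown to be non-compliant with important study procedures", where the investigator and the contracting entity both judge that the patient will not adhere in future. Those patients are among the feasibility failures.

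Protocol 1.3 says that, if successful, this type of design could be used in Phase 2 and 3 trials. That decision needs the failure rate as well as the quality of what arrived.

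**Working it through.** **The plan's own figure.** 80% of 24 hours is 0.80 × 24 = 19.2 hours, which matches SAP 7.5.2.

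**Inputs.** N = 50 expected recordings at a visit is an assumption, based on the approximately 50 evaluable subjects in Protocol 3.1. The number absent (k) and the observed mean (m) are also assumed, because the documents give neither.

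**Mean.** The plan reports m over the N − k available recordings. Over all expected recordings, with absent ones at 0%, the mean is m × (N − k)/N. The difference is m × k/N.

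| Absent of 50 | Plan reports | Absent scored 0% | Difference (points) |
|---|---|---|---|
| 0 | 90.0% | 90.0% | 0 |
| 2 | 90.0% | 86.4% | 3.6 |
| 5 | 90.0% | 81.0% | 9.0 |
| 10 | 90.0% | 72.0% | 18.0 |
| 15 | 90.0% | 63.0% | 27.0 |

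With 5 absent and m between 85% and 95%, the difference is 8.5 to 9.5 points.

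**Median and quartiles.** The formula above is for the mean only. These statistics are conditional in the same way, but their shift depends on the distribution. If every available recording were at 90%, the median would stay at 90% even with 15 of 50 scored 0%. The lower quartile would fall to 0% in that case, because 15/50 = 30% is more than a quarter.

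**The percentage with at least 80%.** Suppose 10 of 50 are absent and 36 of the 40 available recordings pass. On available recordings the result is 36/40 = 90%. On the Entered Set it is 36/50 = 72%. The default in SAP section 7 gives 72%. The endpoint-available wording in Protocol 7.3 would give 90%. SAP 7.5.2 does not say which applies.

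**Recordings against the completion item.**

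| Visit | Recording scheduled (flow chart) | Completion item (SAP 7.5.2) |
|---|---|---|
| 2 | yes | not listed |
| 3 | no | listed |
| 4 | yes | listed |
| 5 | yes | listed |
| 6 | yes | not listed |

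Two of the four scheduled recordings, including the Week 12 one, have no completion count under their own visit. The item also asks about completing the recording, not uploading it. No endpoint in the visible text counts uploads.

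**The case against.** The strongest reply is that the plan already shows the failures. Much of this stands:

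- A reader might infer that failed recordings vanish from the whole endpoint. They do not. By default the 80% summary keeps every Entered Set patient in its denominator.
- The fixed 24-hour divisor already penalises short or partly unreadable recordings.
- N is printed beside each summary (SAP section 7), and all individual data are listed (Protocol 7.2.1).
- The endpoint is defined per recording, so a mean over existing recordings is a legitimate measure of yield. Scoring absences as 0% mixes yield with completion, so it belongs beside that mean and should not replace it.
- The SAP does not say in words that only uploaded recordings are averaged. This follows from the data flow and the missing-data rules. Whether an attempted recording with nothing readable is entered as 0 hours or as missing is not stated.

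Three further readings are tempting but unsupported. The first is that the gap widens at later visits: no figure shows this, and Protocol 3.3.4 tries to keep patients in the study. The second is that uploads achieved with help should not count. Protocol 4.3 builds that help in: if no upload notice arrives, "the site should contact the patient to assess whether the patient requires assistance with any elements of the 24 hour cough recording and upload". Patient-performed need not mean unaided, and the documents do not say that assistance is stored as analysable data. The third is that every missing recording is an upload failure, which would wrongly include death and withdrawals unrelated to the device.

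What remains unanswered is that N alone does not separate non-recording, failed upload and withdrawal. The completion item does not fill the gap, because its visits do not match the schedule and it does not ask about upload.

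**Conclusion.** The point holds for the by-visit mean, median and quartiles. They are conditional on a readable recording existing, so they do not by themselves answer the upload objective. The mean overstates the all-expected figure by the observed mean times the share absent: 9 points at a 90% mean with 5 of 50 absent, and nothing if no recording is absent. The actual size cannot be known from the documents.

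It does not hold for the percentage with at least 80% analysable data, provided the SAP default denominator is used. Because Protocol 7.3 pulls the other way, that denominator should be confirmed. The absence of an upload count and the mismatch in the completion item's visits are separate gaps, and both can be read directly from the text.

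The conclusion assumes that an absent recording is stored as missing and not as 0 hours.

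**What to change.** In SAP 7.5.2:

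1. Add a by-visit summary in which an expected recording with no readable data is scored 0%. Include patients discontinued for non-compliance or because they could not do the procedures. Show death and unrelated withdrawal separately. Keep the available-case summary beside it.
2. State that the percentage with at least 80% analysable data uses the Entered Set as denominator.
3. Report the number and percentage of scheduled recordings successfully uploaded at Visits 2, 4, 5 and 6.
4. Reconcile the visits in the completion item with the flow chart.

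The cost is one extra summary, one upload count and a lower stated feasibility figure. No patient procedure is added. Protocol 3.3.4 has discontinuation reasons recorded in the CRF, but Protocol 6.1 lets patients withhold the reason for withdrawing consent. A line for withdrawals of unknown reason is therefore needed. The documents do not say whether the upload e-mail notices are kept as data, so the source of the upload count must be settled before the table is specified.

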Made of administration			
Mode of administration	I ranscutaneous - adheres to chest wall		
Comparator product(s)	Not applicable		
Duration of assessment	12 weeks		
Statistical methods	Descriptive statistics will be presented for all primary and secondary		
	endpoints. Additionally, CC/hour will be log transformed and		
	summarized in terms of geometric mean and 95% confidence		
	intervals.		

Page 4 of 71

Proprietary confidential information © 2022 Boehringer Ingelheim International GmbH or one or more of its affiliated companies

FLOW CHART

Study Periods	Screening*	Baseline* Visit	Remote Study Visits				EoS Visit
Visit	1	2	3	4	5	6	7/EoS
Days	- 1 wk	1	3	28	56	82	84
Time window for visits			+ 2 days	$\pm 5 \text{ days}$	$\pm 5 \text{ days}$	- 2 days	$\pm 5 \text{ days}$
Informed consent	Х						
Review of in-/exclusion criteria	Х						
Demographics	Х						
Smoking Status/history	Х						
Medical history (Comorbidities)	Х						
Pregnancy status (where available)	Х						Х
COVID-19 history (including vaccination status)	Х						
Non IPF Pulmonary Fibrosis (including ILD diagnosis category) or IPF	Х						
Progressive Pulmonary Fibrosis Phenotype (Y/N)	Х						
Concomitant therapy (including prescription medications for Pulmonary Fibrosis)		Х		Х	Х		Х
Historical Pulmonary Function Tests (FVC & DLCO) ²	Х						
Historical HRCT Pattern ³ (UIP, Probable UIP, Indeterminate for UIP, Inconsistent w/UIP)	Х						
Physical examination		Х					Х
Vital signs ⁴		Х					Х
SpO ₂		Х					Х
In-Office Spirometry ⁵		Х					Х
Distribute & provide instruction on cough monitor		Х					
Distribute & provide instruction on home spirometer		Х					
Home Spirometry			X ^{7,9}	Х	Х	X ^{7,9}	
Reporting of AEs/SAEs ¹⁰ & Unscheduled clinical visits		Х		Х	Х		Х
Videoconference remote visit				Х	Х		
24-hour cough monitor recording ¹¹		Х		X ¹¹	X ¹¹	X ¹¹	
24-hour cough monitor data upload ¹²		Х		Х	Х	Х	
Remote Procedures Compliance Check 13							
(Home spirometry, Videoconference remote visit (V4, V5), Cough recordings)			Х	Х	Х	Х	
Return of cough monitor & home spirometer							Х
Patient survey regarding use of cough monitor and home spirometer							Х

Boehringer Ingelheim BI Study No.: 1490-0005 c39406431-01

Protocol

Proprietary confidential information © 2022 Boehringer Ingelheim International GmbH or one or more of its affiliated companies

Study Periods	Screening*	Baseline* Visit	Remote Study Visits			EoS Visit	
Visit	1	2	3	4	5	6	7/EoS
Days	- 1 wk	1	3	28	56	82	84

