Completion of patient participation							х

*Screening and Baseline Visit can occur on the same day.

- Most proximate historical FVC & DLCO within 6 months and most distant FVC & DLCO within 12 months should be recorded
- 3) Most proximate historical HRCT performed within the previous 12 months
- 4) Measurements of vital signs should precede blood sampling
- 5) Site personnel should confirm that FVC continues to meet eligibility criteria for study inclusion prior to preceding with additional study procedures
- Patients will need to complete home spirometry within 72 hours, but not on the same day as Visit 2/Baseline study visit.
- 8) Patients will need to complete home spirometry in the 72 hrs preceding the day of Visit 7/EoS
- 9) Efforts should be made to perform spirometric measurements at approximately the same time of the day, at least within the same half-day (morning vs afternoon).
- 10) As described in Section 5.2.6.1.1
- 11) 24-hour cough recording should be initiated immediately following the end of the remote visit.
- 12) 24-hour cough recording data upload should occur immediately after completion of 24-hour CC recording. Patients should place the biosensor on the charger next to the study provisioned mobile phone to allow for data to upload.
- 13) Study personnel conducting the visit will review whether the intended procedures for the visit have been completed. If not, the study team will inquire as to whether the patient requires assistance with any specific aspects of the visit. Site staff will receive notification via email each time a patient completes a cough count recording with successful data upload. If the site does not receive this type of notification, the site should contact the patient to assess whether the patient requires assistance with any elements of the 24 hour cough recording and upload.

 P4U6451-U1
 Protocol
 Page 6 of 71

 Proprietary confidential information © 2022 Boehringer Ingelheim International GmbH or one or more of its affiliated companies

TABLE OF CONTENTS

TITLE PA	AGE	1
PROTOC	OL SYNOPSIS	2
FLOW CI	HART	4
TABLE O	PF CONTENTS	6
ABBREV	IATIONS AND DEFINITIONS	9
1.	INTRODUCTION	.12
1.1	MEDICAL BACKGROUND	.12
1.2	DEVICE PROFILE	.13
1.3	RATIONALE FOR PERFORMING THE STUDY	.14
1.4	BENEFIT - RISK ASSESSMENT	.14
1.4.1	Benefits	.14
1.4.2	Risks	.15
1.4.3	Discussion	.15
2.	STUDY OBJECTIVES AND ENDPOINTS	.16
2.1	MAIN OBJECTIVES, PRIMARY AND SECONDARY ENDPOINTS	.16
2.1.1	Main objectives	.16
2.1.2	Primary endpoint(s)	.16

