2.1.3 Secondary endpoint(s)

Secondary endpoints include:

- Change from baseline in CC/hr at Week 4, Week 8, Week 12.
- FVC (mL) at baseline
- FVC (mL) at Week 12
- Change from baseline in FVC (mL) at Week 12
- Feasibility of remote cough data capture (defined as % of analysable data per 24-hour recording)
- Feasibility of hybrid study design (successful completion of all elements of remote visit)

 406431-01
 Protocol
 Page 17 of 71

 Proprietary confidential information © 2022 Boehringer Ingelheim International GmbH or one or more of its affiliated companies
 Proprietary Confidential information © 2022 Boehringer Ingelheim International GmbH or one or more of its affiliated companies

 406431-01
 Protocol
 Page 18 of 71

 Proprietary confidential information © 2022 Boehringer Ingelheim International GmbH or one or more of its affiliated companies
 Proprietary Confidential information © 2022 Boehringer Ingelheim International GmbH or one or more of its affiliated companies

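### Hybrid-visit success in SAP 7.5.2 leaves out the scheduled cough data upload and lists the wrong visits for the recording question, so a remote visit can count as complete with no cough data received

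*SAP*

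**What the plan says.** Protocol 2.1.3 defines the endpoint as "Feasibility of hybrid study design (successful completion of all elements of remote visit"). Protocol 2.1.1 lists a separate secondary objective: "Assess feasibility of patient performed remote cough data upload".

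The flow chart has a row for the 24-hour recording and another for "24-hour cough monitor data upload". For the remote visits, both rows are marked at V4, V5 and V6. Footnote 12 makes upload a later step by the patient: "24-hour cough recording data upload should occur immediately after completion of 24-hour CC recording".

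SAP 7.5.2 gives the scoring rule: "Successful completion of a remote visit will be based on the questions on the home study procedures eCRF". It then lists three of them:

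- The spirometry item reads "Was home spirometry performed? (Visit 3, Visit 4, Visit 5, Visit 6") and covers all four remote visits.
- For the video call, the item is "Was the videoconference televisit completed? (Visit 4, Visit 5"), which agrees with the flow chart.
- The cough item is worded "Was the 24 hour cough recording completed? (Visit 3, Visit 4, Visit 5") and says nothing about upload.

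The SAP tabulates each element, and all elements together, by visit. In the same section it derives the percentage of analysable data per recording and counts patients with at least 80% (19.2 h). That result does not feed into visit success.

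**The concern.** The endpoint says all elements, but a scheduled element with its own secondary objective is not scored. A patient can finish the recording, never get the data off the sensor, and still have every listed question answered yes. The visit list adds a second gap: V6, which supplies the Week 12 cough count, has no cough question at all.

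The protocol's rationale (section 1.3) says that, if successful, this type of design could be used in Phase 2 and 3 trials. For that purpose a remote visit is useful when its cough data arrive. As scored, the hybrid-design table and the data-capture table can disagree about the same visit, and the SAP does not say how to read the two together.

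**Working it through.** **1. The plan's own figure.** 80% of a 24-hour recording is 0.80 × 24 = 19.2 h, as SAP 7.5.2 states.

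**2. Schedule against scoring.** This counts the device and video procedures that the patient carries out at remote visits.

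| Visit | Scheduled in the flow chart | Asked in SAP 7.5.2 | Scheduled but not scored |
|---|---|---|---|
| V3 | spirometry | spirometry, recording | none |
| V4 | spirometry, videoconference, recording, upload | spirometry, videoconference, recording | upload |
| V5 | spirometry, videoconference, recording, upload | spirometry, videoconference, recording | upload |
| V6 | spirometry, recording, upload | spirometry | recording, upload |

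Scheduled elements: 1 + 4 + 4 + 3 = 12. Scheduled elements that are scored: 1 + 3 + 3 + 1 = 8. The four not scored are three uploads and the V6 recording. The V3 recording question matches no recording scheduled at V3.

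**3. The V3 item.** It may look back to the recording started at V2. Protocol 6.1 has the site check the prior recording at V5, so a look-back reading is possible. On that reading the V5 question would refer to the V4 recording, and the recording started at V6 would still not be covered. The list may also simply be one visit out. The text does not settle which.

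**4. What the rule allows.** At V4 or V5, three yes answers give full success whatever the upload status. At V6, one yes to spirometry gives full success with neither a recording nor an upload.

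**5. Possible size.** The documents give no upload rates, so this is an illustration. Let S be the success rate as the SAP scores it, and u the share of those visits whose cough data were uploaded, assumed to be 80% to 100%. Success including upload is S × u, and the relative reduction is 1 − u.

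| u | Relative reduction | S = 100% becomes | S = 90% becomes |
|---|---|---|---|
| 100% | 0% | 100% | 90.0% |
| 95% | 5% | 95% | 85.5% |
| 90% | 10% | 90% | 81.0% |
| 80% | 20% | 80% | 72.0% |

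The absolute reduction is 0 to 20 points at S = 100% and 0 to 18 points at S = 90%. With 50 patients, u = 90% at S = 100% means 45 successes instead of 50.

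**The case against.** **The SAP follows a list in the protocol.** The compliance-check row of the flow chart names the same three procedures without upload. This explains the SAP wording. However, that row is a visit checklist and the endpoint refers to all elements. The row also includes V6, and footnote 13 tells sites to contact the patient when no notice of successful upload arrives.

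**Completed may already mean uploaded.** Under Protocol 4.3, sites are emailed when a recording is completed with successful upload. Some sites may answer yes only after that email. This stands as a limit: the visit can count as a success, but it need not. The eCRF completion instructions are not in the documents, and the SAP question does not mention upload.

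**Upload failure is visible elsewhere.** This largely stands. SAP section 7 takes percentages over all subjects in the set by default, with or without data, so a recording never uploaded should fall outside the group with at least 80%. The mean percentage is less safe, because missing data are not imputed (Protocol 7.3) and such a recording may drop out. The failure can be seen in the study but not in the endpoint that claims to cover all elements.

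**Usable FVC.** A reader might infer that spirometry should count only with an acceptable FVC. The protocol does not make that a condition of completing a remote visit. Home sessions are video-supervised. Electronic transmission and vendor overread appear in the on-site spirometry text of Protocol 5.1, and the visible documents do not show that graded home data are held.

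**Conclusion.** The upload omission and the visit-list mismatch are both established by setting SAP 7.5.2 beside the flow chart. The rule as written can score V4 or V5 as fully successful with no uploaded cough data, and V6 on spirometry alone.

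The size is unknown. The range of 0 to 20% in relative terms rests wholly on assumed upload rates of 80% to 100% among visits scored complete. It covers the upload element only, and zero is possible if sites already equate completion with upload.

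Two stronger readings are not supported:

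- A reader might infer that the endpoint can only overstate feasibility. A 20-hour recording is 20/24 = 83.3% and passes the 80% threshold, yet a site could answer no to whether the 24-hour recording was completed. An unscheduled V3 question could also lower V3 success.
- A reader might assume 95% yes on each of three items (0.95³ = 0.857) and usable-data rates of 95%, 90% or 80% for each device. Success is then 0.774, 0.694 or 0.549, an overstatement of 8 to 31 points. None of those rates is in the documents, and the calculation rules out zero and brings in the FVC condition that the protocol does not set.

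The study is descriptive with no feasibility threshold, and the primary endpoint is unaffected. The change is worth making because the endpoint as scored does not match its definition.

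**What to change.** In SAP 7.5.2:

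1. Count the cough element at V4, V5 and V6 as met only if the recording was uploaded with at least 80% (19.2 h) readable time. Treat a missing upload as not met.
2. Align the recording item with the flow chart by adding V6. State whether the V3 item refers to the recording started at V2; if so, report it as that recording and not as an element of V3.
3. Leave the spirometry and videoconference elements as eCRF answers.
4. Keep the eCRF-only percentages as a second column, so that reported completion and data received can be compared at each visit.
5. Report a version requiring an acceptable home FVC only as supportive, and only if home-spirometry quality data are already available.

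The cost is SAP wording and a small merge of readable recording time, already derived for the neighbouring endpoint, with the eCRF answers. It needs no new procedure and adds nothing for patients. The reported success percentage may be lower.
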